**In vivo Three-Dimensional Determination of
OA Brace Effectiveness**

[name]
 University of Tennessee
 [name]
 [name]
 [name]
 [contact]
 [contact]
 Email: [contact]

In vivo knee kinematics will be assessed for 20 subjects that have been clinically diagnosed with substantial unicompartmental osteoarthritis (OA) by one of the surgeons of Colorado Joint Replacement; this is the location from which participants will be recruited.

Enrollment will be increased to 24 subjects to account for any dropouts. Medial joint space narrowing will be clinically assessed in all patients on standing anteroposterior radiographs. The objective of this study will be to analyze subjects with symptomatic unicompartmental osteoarthritis under in vivo dynamic, weight-bearing conditions using video fluoroscopy to determine if present-day OA knee braces provide separation of the femoral condyle from the tibial plateau, thus avoiding excessive loads on the degenerative compartment.

The study will be submitted to Western IRB (WIRB); the University of Tennessee's IRB and Centura Health/Catholic Health Initiatives (for Colorado Joint Replacement/Porter Adventist Hospital) have waived oversight to WIRB. The required Reliance Agreements will be included with this submission to WIRB.

We will use the following inclusion criteria to recruit participants for this study:

1. Must be a patient of Colorado Joint Replacement.
2. Must be diagnosed with marked unicompartmental degenerative joint space narrowing.
3. Bilateral subjects may not be included in the subject population.

Exclusion criteria:

1. Pregnant, potentially pregnant or lactating females. To satisfy radiation protocol, each female subject will be asked if she is pregnant, or possibly could be pregnant. A pregnant person will not be allowed to participate in the study.
2. Subjects who are unable to perform normal walking.
3. Subjects who are unwilling to sign Informed Consent/ HIPAA documents.
4. Does not speak English.

Investigators

[name], Ph. D. (PI)
 [name] (Co-PI)
 [name] (Sub-I)
 [name], Ph. D. (Sub-I)
 [name] (Sub-I)
 [name] (Sub-I)

Study locations

Subject Recruitment will take place at Colorado Joint Replacement:
Colorado Joint Replacement
[name]
[name]
[contact]

Fluoroscopic exams, ultrasound exams and CT exams will be performed on all 20 (or possibly 24) subjects at: Porter Adventist Hospital

[name]
[name]
[contact]

Satellite sites:

Analysis will take place at the University of Tennessee's Center for Musculoskeletal Research laboratories:
Science and Engineering Research Facility
[name]
[name]

CMR administrative offices:

[name]
[name]
[name]

Recruitment

Patients of Colorado Joint Replacement in Denver, Colorado will recommend eligible subjects for recruitment who have been clinically diagnosed to have marked unicompartmental degenerative joint space narrowing. Since there are no inclusion criteria other than being a patient of Colorado Joint Replacement and having unicompartmental OA, review of patient medical files prior to contacting about participation is not necessary. No inclusion/exclusion checklists will be used to ensure eligibility since no other criteria must be met other than being a patient of Colorado Joint Replacement, having the unicompartmental degenerative joint space narrowing, being able to speak English and perform normal walking. The surgeons of Colorado Joint Replacement will be aware of which of their patients have this joint condition. Even though a HIPAA waiver for recruitment will not be necessary, patient medical files will need to be accessed in order to acquire contact information for each potential subject.

[name] will contact the patients to explain the study using an approved script and inquire as to whether or not they are interested in participating. A partial waiver of HIPAA has been included for this. The surgeons of Colorado Joint Replacement may also bring the study to patients' attention during regular office visits and will use language similar to that in the script. If a patient is agreeable to participate, s/he will be scheduled to visit Porter Adventist Hospital on the day of data collection. On this scheduled day, UT researchers will travel to Porter to collect the kinematic data of participants' knees under fluoroscopic surveillance using a C-arm fluoroscopic unit while subjects perform normal treadmill walking in the frontal plane. The fluoroscopic images will be stored on password protected computer workstations for subsequent analysis.

Data Collection

Fluoroscopy

On the scheduled day of data collection, there will be at least two UT researchers present (which could also include the PI), as well as a study PI, (Drs. [name], [name]; [name], [name], [name], [name] [Sub-Investigators]) to conduct the fluoroscopic evaluation. Each subject will be asked to perform gait without the assistance of an offloading brace (Figure 1a). Then, each subject will be fitted with a Breg, off-the-shelf OA brace and will perform normal gait while under fluoroscopic surveillance (Figure 1b). To ensure each brace was fitted properly, Breg will be asked to send either a sales representative or an engineer to the evaluation site. Therefore, the sales representative or engineer will be asked to fit their brace on each of the subjects. This individual will sign a pledge of confidentiality.

[figure not shown]

Figure 1. Subject on a treadmill perform gait without a brace (a) and with a brace (b).

A Radiation Technician (RT) employed by Porter Adventist Hospital will perform the actual fluoroscopy procedure, following the subjects' OA knee with the unit as the activity is performed with and without the OA brace; only the knee joint (from the fluoroscopy machine) will be recorded on the fluoroscopy footage. The UT researchers, graduate research assistants (GRAs), which may include any of the following - [name], [name], [name], [name], [name] – will be present, although they will not perform the actual fluoroscopy procedure. They will be present during the fluoroscopy procedure to walk subjects through the activities, answer any questions that may arise, ensure data collection equipment is set up as needed and serve as consultants to the RT.

Any of these UT individuals, or study staff from Colorado Joint Replacement, will consent the participants. They will meet with each potential participant individually to make sure s/he has been properly informed of the procedures and to help with any of the IC form. CMR researchers will inform all subjects that they do not have to participate and are free to leave if they wish and will answer any questions subjects may have about the study. Participation is entirely voluntary.

Participants will be asked to practice the activity to ensure they can comfortably complete it and experience no pain with the fluoroscopy machine off (no radiation). The practice portion of the data collection without radiation will not be video-recorded.

Multiple trials of each activity may be conducted to ensure usable images have been acquired to complete the study. Radiation time will be kept as low as reasonably achievable (ALARA) and will not exceed two minutes. The RT will start the fluoroscope just prior to the subject beginning the activity trial and will stop the fluoroscope immediately after the subject completes each activity trial to ensure that the subject is not exposed during idol periods. On-time will be recorded on the subject's IC, as well as any output the fluoroscopy unit is able to provide.

In addition to fluoroscopy video, subjects will be videotaped from the shoulders down (to maintain subject anonymity) while performing the activities (live feed perspective). The speed level of each trial will be based on the comfort level of the subject. One of the researchers will be ready and in close proximity to assist each subject in case the participant requires help. This precaution will be practiced for all participants, regardless of physical wellbeing, age or prior results; no assumptions will be made as to any participant's capabilities. The participant will be allowed to rest as necessary and be instructed to stop the activity at the first sign of pain.

The fluoroscopic and video footage for the study activities will be stored on digital video files on a secure computer workstation and stored securely by UT researchers. It will then be uploaded onto the secure CMR database by these researchers. Once the data has been uploaded, identifiers are removed from the data automatically by the database, and a study and subject-specific identifier will be assigned to each subject.

JointVue three-dimensional ultrasound

Since the skeletal geometry is different for every person, computer aided design (CAD) models of the femur and tibia will be created for each specific subject. In order to create these CAD models, each subject will be asked to undergo a three-dimensional (3D) ultrasound using the JointVue proprietary software to reconstruct 3D femoral and tibial bones (Figure 2). A representative from JointVue will be present during data collection to conduct the ultrasound procedure in order to create the CAD models. This individual will sign a statement of confidentiality.

Study data will then be uploaded onto a secure server that University of Tennessee researchers will use to conduct the kinematic analysis using a model-fitting approach, the relative pose of knee implant components will be determined in 3D from a single-perspective fluoroscopic image by manipulating a CAD model in 3D space.

Using a model-fitting technique, the 3D bones will be overlaid onto the fluoroscopic images to determine amount of medial OA offloading. Successive fluoroscopic images of each subject's stance phase, with and without the OA brace, will be downloaded to a computer. Images will be captured at five instances during stance-phase of gait: heel strike, 33% of stance phase, mid-stance, 66% of stance-phase and at toe-off. A comparative analysis will be conducted for each subject while wearing the OA brace and with their non-braced test. Then, the amount of medial condylar separation will be assessed for each subject.

[figure not shown]

Figure 2. Example of 3D bone creation.

CT Scan

Participants will be asked to schedule a CT scan at Porter Adventist Hospital at their convenience within 1 month of the initial data collection day. To ensure subject safety, CT will be limited to the affected knee and the rest of patient's body will be protected from radiation with lead protection. The CT scan will be limited to the study knee and will image 6 inches distal on the tibia and 6 inches proximal on the femur.

Private Health Information/Medical Record Data

It is not anticipated that the subjects' medical files should need to be accessed for any PHI for the study for recruitment or for the conduct of the study itself. However, contact information from patient files will be acquired for inquiring as to whether or not patients would be willing to participate. The only subject-specific data that will be necessary will be measurements of medial condyle separation from the medial tibial plateau for each subject with and without a brace. Researchers will acquire the measurements with the brace while they are conducting the data collection. Researchers may also acquire the subjects' medial condyle separation without the brace while they are present for data collection. However, if this is not possible or time does not permit, Colorado Joint Replacement staff may send that information to UT researchers via secure transfer (e.g., UT Vault).

The subject data – fluoroscopy frames, video footage and ultrasound– will be uploaded and stored on CMR's secure server for use in this and future studies (if participant permission is obtained via IC) by the researcher(s) who attend data collection or appointed by [name]. Once data has been uploaded, the database automatically removes subject identifiers and assigns an ID for each subject. Only these files of de-identified data are now available for researchers to review and analyze. Only [name], [name] and [name] have access to the 5-Breg OA Brace Effectiveness V1.1 protocol

identifiable data that was originally uploaded by the GRA, as it remains in a password-protected portion of the secure server. Only [name] and [name] can grant access to this identifiable password-protected portion of the database by changing a user's level of authentication with different privilege levels.

Researchers would like to retain this study data in our secure database so as to continue to add relevant, current data to our digital collection to help us work with manufacturers in the future to create better orthopaedic products. Participants will be asked if their study data may remain a part of the CMR data collection for use in future studies in the IC. Likewise, should a subject choose to withdraw from the study, s/he will have the option as to whether or not data collected from them at the point of withdrawal may be used for data analysis or if their information should be destroyed from CMR records; subjects choosing to withdraw will be asked to complete a Revocation of Consent wherein they may indicate their preference regarding the data collected from them.

On the day of data collection, the list of patient names will be given to UT researchers and the researchers will generate subject-specific identifiers for each participant. A table will be generated for this study, indicating the participant's name and generated ID number; this table with subject names and corresponding ID numbers will be provided to Colorado Joint Replacement staff, so the staff will be aware of which identifier is linked with each subject. If necessary (i.e., time not permitting during data collection; researchers unable to collect measurement), Colorado Joint Replacement staff may relate the measurements of medial condyle separation from the medial tibial plateau for each subject without a brace securely to UT researchers via the UT Vault <https://vault.utk.edu/>.

SPECIFIC RISKS AND PROTECTION MEASURES

1. Fluoroscopic Procedures

As with every clinical study, there may be some risks. However, doses of radiation exposure received will be much lower than those known to produce detectable health effects. Previously reported literature shows that fluoroscopy-based procedure (angiography) on the lower limb result in a typical effective dose of 0.83 mSv per min (0.083 rem per min) (Verdun¹). Mettler, et al. have reported that the typical effective dose for a conventional knee procedure is 0.005 mSv (0.0005 rem)². According to either estimate, the additional risk of a fluoroscopic procedure involving the knee ranges between "Negligible" to "Low" for a 2 minute exam (Verdun). A previous fluoroscopy TKA study conducted at another hospital with a 2 minute on-time limit shows that the average effective dose was 0.14 mSv (0.0014 rem) with a maximum dose of 0.27 mSv (0.027 rem). The additional risk for all subjects in this previous study would be considered "Negligible." To account for subject variability and differences in imaging techniques, all subjects enrolled in this study will receive less than 2.0 rem. 2.0 rem is considered "Low" risk. It is unlikely that anyone in this study will approach the 2.0 rem limit. Since the fluoroscopy data will be collected in one session, there will only be one day in which the participants will be exposed to this amount of radiation.

2. CT Scan

In addition to the radiation exposure from the fluoroscopy procedure, all subjects will be exposed to radiation from the CT scan of the knee (which is considered an "extremity"), estimated at 0.01 rem, according to the American Nuclear Society's Radiation Dose Chart,

<http://www.ans.org/pi/resources/dosechart/> (Attachment 4). The radiology department at Porter Adventist hospital uses a software program call Caredose that automatically keeps the dose as low as possible on all CT exams. Insofar as the amount of time for the CT scans taking place, we estimate approximately 30 minutes for the exam itself.

In conclusion, a participant who will be fluoroscoped for less than two minutes will be exposed to a maximum amount of only 2.0 rems of radiation. This means that the maximum total exposure rate will be less than 2.0 rems per subject for the entire experiment. The participant's knee joint will be fluoroscoped using negligible to low risk levels of radiation according to published literature.

The participant has the right to stop the procedure at any time; researchers or the RT can end the procedures at any time if they feel the participant is at risk, but the participant can choose to remain in the study if s/he feels that there is no risk to her/his surgical procedure or recuperation.

3. Participant Confidentiality

The investigators will ensure subject confidentiality to the extent that is permissible by law is maintained throughout the study and after. Researchers not notated as Investigators of this study that have access to subjects during data collection will sign pledges of confidentiality. Complete confidentiality cannot be guaranteed.

Computer Database

As noted, on the day of data collection, the list of patient names will be given to UT researchers and researchers will generate subject-specific identifiers; Colorado Joint Replacement staff will be provided with this list of subject names and corresponding generated identifiers. These assigned identifiers will be uploaded into an excel spreadsheet created by UT researchers. Colorado Joint Replacement staff will be aware of each subject's respective identifier from the table provided to them on the day of data collection after UT researchers generate the subject-specific identifiers

Researchers present during data collection or appointed by [name] will upload the subject data, including fluoroscopy, video and ultrasound, into the CMR digital data collection. Consequently, student researchers in CMR who assist in data analysis cannot access subject-specific information. All participant queries (lookups) generate the participant identification number and no subject identifiers. No identifiable images exist in the database. This study data will be kept indefinitely on the secure CMR database for possible future research (with the permission of each participant – requested in the IC). In the case of participant withdrawal from the study, the Revocation of Consent that the participant will be asked to complete requests that the participant indicate whether or not data collected prior to withdrawal may be used for data analysis purposes, or if it should be removed from the CMR data collection completely and destroyed.

Hard Copy

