Informed consent will be obtained prior to any procedures being conducted. Subjects who are agreeable to participate will be scheduled to visit Porter Adventist Hospital on the day that UT researchers will travel there for data collection. Appointed staff from Colorado Joint Replacement and/or UT researchers will be responsible for consenting the participants, giving them ample time to review and complete the forms and assist the participants with review of the documentation, if the participants are unable to read the form on their own. Only upon signed consent will the subject be allowed to participate in the study. If the subject chooses to be removed from the study after participating, his/her video, fluoroscopy footage and ultrasound data that was collected will be managed according to the subject's response on the Revocation of Consent form. A copy of his/her Revocation of Consent will be attached to his/her IC and placed in a separate, secure file for IRB review. These consent forms will be stored at UT, Knoxville and will be accessible by only the aforementioned personnel.

Drs. [name] and [name] will not be present during the consenting process to avoid possible subject coercion to participate. Subjects may contact Colorado Joint Replacement with any questions they may have.

From previous studies, we have determined that it takes approximately 15 minutes to consent a subject and answer any questions that s/he may have. We have also estimated approximately 20 minutes for researchers to guide the subject through the steps of the procedure, allow the subject

to practice the activity and then to actually perform the activity under fluoroscopic surveillance; actual radiation exposure will be up to, but not more than two minutes. The ultrasound portion of the data collection should take approximately 10 minutes. We have estimated a total time of approximately 45 minutes for each subject to be consented and complete the fluoroscopy and ultrasound procedures.

ATTACHMENT 1

Table 2
Generic Dose-Area Products, Conversion Factors, and Effective Doses at Angiography in a Standard Adult Patient

Examination*	Fluoroscopy time (min)	Dose-Area Product (Gy • cm ²)	Conversion Factor (mSv/Gy • cm ²)	Effective Dose (mSv)
Cerebrum	12	75	0.04	3.0
Coronary arteries	4	75	0.20	15.0

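### Every subject walks unbraced first and braced second, so a step change between the two walks cannot be separated from the brace effect; separately, treadmill speed is not stated to be recorded

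*Protocol*

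**What the plan says.** The order is in the Protocol, Data Collection, Fluoroscopy. First: "Each subject will be asked to perform gait without the assistance of an offloading brace (Figure 1a". Next: "Then, each subject will be fitted with a Breg, off-the-shelf OA brace and will perform normal gait while under fluoroscopic surveillance". Neither document randomises or counterbalances this sequence, or repeats the unbraced walk after the brace.

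The same section has several provisions that bear on drift between the walks:

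- Repeats are optional and serve image quality: "Multiple trials of each activity may be conducted to ensure usable images have been acquired to complete the study".
- Practice with the beam off: "Participants will be asked to practice the activity to ensure they can comfortably complete it and experience no pain". The text does not say whether practice is braced, unbraced or both.
- Rest and stopping: "The participant will be allowed to rest as necessary and be instructed to stop the activity at the first sign of pain".
- Imaging time: "Radiation time will be kept as low as reasonably achievable (ALARA) and will not exceed two minutes".
- Speed: "The speed level of each trial will be based on the comfort level of the subject". The section says that fluoroscopy on-time and the unit's output are recorded. Neither document says this of treadmill speed.

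The Protocol's section on obtaining informed consent gives the time scale: "We have also estimated approximately 20 minutes for researchers to guide the subject through the steps of the procedure", a figure that also covers practice and the imaged walks.

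The ultrasound section reads five stance-phase instants per condition and compares each subject with and without the brace. The section on Private Health Information/Medical Record Data lets clinic staff supply the unbraced value if it cannot be obtained on the day. The SAP's Data Analysis section treats the data as two cohorts, lists Student's t, Welch and Mann-Whitney tests, and has no period or speed term.

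**The concern.** The study asks whether the brace separates the femoral condyle from the tibial plateau, and its only contrast is braced against unbraced within the same person. With a single order, that contrast is the brace effect plus whatever else changed between the first and second walk. A subject may be more used to the treadmill by the second walk, more tired, or in more pain. Such a change could imitate a brace effect or hide one. No choice of test removes it, and a step change cannot be recovered from the data afterwards.

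Speed is a separate matter. It is chosen by comfort for each trial, so it may differ between conditions. It is uncontrolled but not aliased with the brace: if it were logged, it could be reported by condition.

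**Working it through.** **Inputs.** From the documents: fixed order; n=20, or 24 to allow for dropouts; alpha 0.05 (two-sided assumed, as sidedness is not stated). Not in the documents, and therefore assumed: the drift, the within-subject correlation rho, and a standardised paired difference of 0.66 for power. The plan gives no power or effect-size figure to reproduce.

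**1. What the contrast estimates.** Let tau be the brace effect and pi the change from first to second block. Under the fixed order, mean(braced − unbraced) = tau + pi. The bias is the whole of pi.

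**2. Is pi separable?** A model at n=20 with 20 subject terms, one brace term and one period term has 22 columns.

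- Fixed order: rank 21 of 22 (25 of 26 at n=24). It remains 21 of 22 with two or three trials per condition, because every repeat stays inside its own block.
- Fixed order, two trials per condition, a linear trial-number trend instead of a step: rank 22 of 22. With times −1.5, −0.5, 0.5, 1.5 and brace coded −0.5, −0.5, 0.5, 0.5, the squared correlation is 2²/(1 × 5) = 0.8. The standard error of the brace effect is therefore multiplied by sqrt(1/(1 − 0.8)) = 2.24, assuming independent trial errors. A true step of 1.00 fitted with this model still gives a brace coefficient of 1.00.
- Order balanced 10/10: rank 22 of 22, and brace and period are uncorrelated.

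**3. Rejection rates with no brace effect, n=20.** Drift is in SDs of the within-subject difference. The paired test uses a noncentral t with 19 df and noncentrality drift × sqrt(20). The unpaired Student's t (38 df) was applied to paired data in 1,000,000 simulations.

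| Assumed drift | 0 | 0.1 | 0.25 | 0.5 |
|---|---|---|---|---|
| SAP's Student's t, rho 0.3 | 2.1% | 3.3% | 10.9% | 43.6% |
| SAP's Student's t, rho 0.5 | 0.7% | 1.3% | 5.3% | 28.6% |
| SAP's Student's t, rho 0.7 | 0.1% | 0.2% | 1.1% | 10.2% |
| Paired t (not in the SAP) | 5.0% | 7.1% | 18.6% | 56.5% |
| Balanced order, paired, period term, no carry-over | 5.0% | 5.0% | 5.0% | 5.0% |

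The unpaired rates are low because that test uses a variance of 2σ²/n for the difference in means, whereas the true variance is 2σ²(1 − rho)/n.

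**4. Cost of balancing.** The estimate is the average of the two sequence means of (braced − unbraced), so pi cancels. Its standard error is 0.5 × sqrt(s²/10 + s²/10) = s/sqrt(20), as in the paired test; only one degree of freedom is lost. At the assumed 0.66, power goes from 79.9% to 79.7% at n=20 (79.3% if dropouts leave 11/9), and from 87.2% to 87.1% at n=24.

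**5. Carry-over.** Suppose a fraction f of the brace effect persists into a later unbraced walk. The two sequence means are tau + pi and tau − pi − f·tau, which average to tau(1 − f/2). For f = 0.1, 0.2 and 0.3 the estimate is 95%, 90% and 85% of tau, and power is 75.6%, 71.0% and 66.0%. This bias, f·tau/2, exceeds the fixed-order bias only if the carry-over is more than twice the drift.

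**The case against.** Unbraced-first is a defensible order for a within-subject device test, since it rules out brace carry-over. If drift is truly near zero, it is the less biased order. The documents quantify neither drift nor carry-over. The walks are short, with practice, rest, a stop at first pain and capped imaging. All of this stands. These provisions may shrink a drift, but they do not make it estimable, so its absence could not be shown from the data.

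Several stronger readings are tempting, and the documents do not support them:

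- **That the plan has a false-positive rate of 19% or 56%.** Those rates belong to a paired t-test that the SAP does not list, at drifts that are assumed. With the SAP's Student's t at rho 0.5, the rate reaches only about 5% at a drift of 0.25 SD.
- **That the result will be biased.** Only the aliasing is established. No drift is documented.
- **That each condition is measured once.** Five stance instants are read and repeats are allowed. The exact statement is one measured block per condition.
- **That the whole drift enters every subject's comparison.** Where clinic staff supply the unbraced value, the comparison need not be first walk against second walk, and randomising order does not help.
- **That speed information is irretrievably lost.** The walks are videotaped, and heel strike and toe-off are identified on fluoroscopy. Stance time or cadence might serve as a proxy, depending on frame timing that the documents do not give.

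**Conclusion.** The concern holds as a design weakness that is cheap to remove. For subjects measured in both conditions at the session, a step change between blocks is completely aliased with the brace effect, and repeat trials do not alter that. This follows from the stated order alone and needs no drift figure. The size and direction of any resulting bias are unknown, and it may be small. The rejection rates illustrate assumed drifts and correlations and are not predictions for this study. Keeping false positives below nominal with the unpaired test does not remove the bias in the estimate.

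The advantage of a balanced order rests on carry-over being no more than twice the drift. Neither quantity is given, so this is a judgement, but carry-over from a briefly worn brace is a modest risk compared with an order effect that can never be examined. The speed point is narrower: the plan sets speed by comfort and does not say that it is recorded.

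**What to change.** - Randomise the order of the two conditions in small blocks, 10/10, or 12/12 if 24 are enrolled.
- In the SAP, specify a paired analysis with a period term and state the no-carry-over assumption.
- For braced-first subjects, use the rest the Protocol already allows after the brace comes off. For unbraced-first subjects, place any braced practice after the recorded unbraced walk.
- Take the unbraced value from the same session. Where the clinic supplies it, flag the subject and repeat the analysis without those subjects.
- Keep the comfortable speed, log treadmill speed for every trial and report it by condition. Treat any speed-adjusted result as exploratory only: comfortable speed may respond to the brace, so adjustment could remove part of its effect.

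The cost is a short Protocol and SAP amendment, a randomisation list and a speed log. No extra subjects, visits, imaging time or brace fittings are needed. The downsides are possible carry-over in the braced-first half, which attenuates the estimate by half the carry-over; the need for the manufacturer's fitter to be present from the start of the session; and sessions that may run slightly longer than the block of about 20 minutes. If the present order is kept, the SAP should give the reason and state the limitation.
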